### 5.4.3 Adverse Event Reporting

All unexpected serious adverse events thought to be related to the study drug, and any unexpected fatal or life-threatening adverse events thought to be related to the study drug will be recorded in the online CRF, reported directly to the coordinating center, and reported to the appropriate IRB shortly following the event per local protocol. In addition, unexpected serious adverse events related to the study drug will be undergo expedited reporting to the DSMB within 7 days of the coordinating center becoming aware of the event. The DSMB will additionally review all adverse events in aggregate after every 50 patients are enrolled.

Adverse events will additionally be reported to the FDA as outlined in 21CFR312.32 and summarized below:

- a. All unexpected fatal or life-threatening adverse events thought to be related to the study drug will be reported to the FDA within 7 calendar-days of when the ACTS team is made aware of the event.
- b. All unexpected serious adverse events thought to be related to the study drug will be reported to the FDA within 15 calendar-days of when the ACTS team is made aware.
- c. All serious unexpected adverse events, and any unexpected fatal or life-threatening events thought to be related to the study drug, will be reported back to all site investigators within 15 calendar-days of the event.
- d. The ACTS team will periodically review all published information relating to the safety of each element of the drug combination. Any concerning safety information obtained from this review, or otherwise obtained (e.g. from unpublished scientific papers), will be reported to the FDA within 15 calendar-days.

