#### **3.3 Exclusion criteria**

Exclusion criteria:

- 1) Member of a protected population (pregnant, prisoner)
- 2) Known history of kidney stones within the past 1 year (not including incidentally noted stones noted on imaging studies)
- 3) End stage renal disease requiring dialysis (hemodialysis or peritoneal dialysis)
- 4) Known history of G6PD deficiency
- 5) Known history of Hemochromatosis
- 6) Comfort Measures Only status
- 7) Anticipated death within 24-hours despite maximal therapy (as determined by the enrolling physician)
- 8) Receiving supplemental vitamin B1 in a dose greater than that contained in a multivitamin (<2mg)
- 9) Clinical indication for steroids (e.g. chronic use) as determined by the clinical team providing this drug
- 10) Clinical indication for ascorbic acid supplementation in any form
- 11) Clinical indication for vitamin B1 as determined by the clinical team providing this drug
- 12) Known allergy to vitamin C, hydrocortisone, or vitamin B1

Justification of Inclusion and Exclusion Criteria: The inclusion criteria were chosen to isolate a septic participant population with high risk of organ injury and death. The exclusion criteria were chosen to minimize the risk of potential harm and to ensure that participants enrolled do not already have chronic end-stage renal failure with a high likelihood of early need for renal replacement therapy. By evaluating this high-risk population (i.e., most likely to die), we will target those most likely to benefit and therefore increase the probability of showing efficacy.

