## 5.4 Safety

### 5.4.1 Definitions

The following definitions will be used:

**Adverse event:** any untoward medical occurrence in a participant to whom a medicinal product is administered and which does not necessarily have a causal relationship with this treatment

**Serious adverse event:** any untoward medical occurrence that at any dose requires inpatient hospitalization or prolongation of existing hospitalization, results in persistent or significant disability or incapacity, results in a congenital anomaly or birth defect, is life-threatening, or results in death

**Unexpected serious adverse event:** a serious adverse reaction, the nature, severity or outcome of which is not consistent with the reference safety information

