### 5.4.2 Specific adverse event data collection

To assess specific and potentially serious adverse events that may be related to the combination of the study medications, we will collect data on the following:

Serious Adverse Event	Definition
Hyperglycemia	Serum glucose >300mg/dl in the first 120-hours after enrollment
Hypernatremia	Serum sodium (> 150 mmol/L) occurring in the first 120-hours after enrollment
New Infection	As determined by the site principal investigator at each site. Should be a new organism or site of infection and believed to be unrelated to the initial presenting infectious source. Many will have the initiation of new antibiotics or a change in antibiotics.
Catheter-site	
Lung	
Gastrointestinal	
Urinary tract	
Other	
Serious allergic reaction	Anaphylaxis or other allergic reaction requiring systemic corticosteroids. Allergic reaction should be related (or suspected to be related) to the study medication
Renal calculus	Development of a renal calculus between enrollment and 30-day follow-up (based on question asked during follow-up phone call).

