#### *8.1.2 Potential harms*

##### **Study Drug**

Vitamin C – Ascorbic acid is a water-soluble essential vitamin that is safe even at high doses. Nevertheless, adverse effects related to high-dose ascorbic acid have been described. These adverse effects include diarrhea/abdominal bloating, increased oxalate excretion, iron overload in participants with hemochromatosis, and hemolysis in participants with G6PD deficiency. We exclude participants with known renal failure, known G6PD deficiency, or known hemochromatosis to limit these potential risks. We will additionally exclude participants with known allergy to ascorbic

acid. Ascorbic acid has additionally been used in at least 3 clinical trials in critically-ill populations without major associated adverse effect.

Hydrocortisone – Hydrocortisone is a well-established medication for the treatment of refractory shock in sepsis. Some studies (e.g. CORTICUS) have found an increased incidence of secondary infection in participants with septic shock who receive steroids. This finding has not been replicated in other large trials of corticosteroids for sepsis. Additional hypothetical risks to the administration of hydrocortisone to participants with septic shock (e.g. increased gastro-intestinal bleeding, muscle weakness, and delirium) have not been found in clinical trials of corticosteroids in sepsis. Finally, hydrocortisone may increase the risk of hyperglycemia and hyponatremia.

Hydrocortisone will not be tapered in this study as prior studies have shown benefit with corticosteroids in septic shock without a taper. In addition, a recent large trial of corticosteroids in septic shock (ADRENAL, NEJM 2018) randomized patients to 7-days of corticosteroids or placebo and did not include a taper. In that trial there was no reported difference in rates of recurrent shock.

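### Sections 5.4.2 and 5.4.3 give no recording rule for a serious, drug-related event that is expected and off the five-item list, so the DSMB's promised review of every adverse event has no matching collection procedure

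*Protocol*

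**What the plan says.** Protocol Section 5.4.3 opens with the recording rule. It covers "All unexpected serious adverse events thought to be related to the study drug, and any unexpected fatal or life-threatening adverse events" when they are thought to be drug-related, and says that these "will be recorded in the online CRF, reported directly to the coordinating center" and sent to the IRB. It then adds DSMB notification within 7 days for unexpected related serious events. It ends the paragraph with "The DSMB will additionally review all adverse events in aggregate after every 50 patients are enrolled". The current SAP text carries the same section.

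Section 5.4.2 is the other stated source of safety events. It says "we will collect data on the following" and lists five categories: hyperglycemia, hypernatremia, new infection (with sub-rows by site), serious allergic reaction and renal calculus.

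Section 5.4.1 defines an unexpected serious event as a serious reaction whose nature, severity or outcome is one "which is not consistent with the reference safety information". The documents do not say what that reference is.

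Section 8.1.2 describes, for vitamin C, "iron overload in participants with hemochromatosis, and hemolysis in participants with G6PD deficiency", and gives, as hypothetical hydrocortisone risks, "e.g. increased gastro-intestinal bleeding, muscle weakness, and delirium". Section 3.3 excludes "Known history of G6PD deficiency".

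**The concern.** Using unexpectedness to decide what is reported quickly is ordinary practice. Section 5.4.3 uses it in the sentence that says what is entered on the CRF at all. Followed as written, that rule leaves out serious reactions that are attributed to the drugs and already described for them, which are reactions a safety board would want counted by arm.

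This matters more here than in many trials. Section 9.2 sets no statistical criteria for stopping on safety and leaves termination to the DSMB's discretion, so the board's tables are the main safeguard. Section 8.1.2 cites only one earlier study of the three drugs together, a retrospective before-after study. Section 6.2.3 has adverse events analyzed in the same way as renal failure, that is by Fisher's exact test. If the set of collected events is undefined, so is the safety analysis set.

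**Working it through.** The plan gives no figure on this point, so there is none to reproduce. The check sets the rules side by side.

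**Step 1. Serious events that are not on the 5.4.2 list**

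| Thought related? | Expected? | CRF recording rule in 5.4.3 |
|---|---|---|
| Yes | No | Stated: CRF, coordinating center, IRB, and DSMB within 7 days |
| Yes | Yes | None stated |
| No | Either | None stated |

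The second row is the gap. It includes a fatal reaction that is related but expected. That participant would be counted in 30-day mortality (Section 5.1.2), but no stated rule records the reaction as a safety event.

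**Step 2. Do other sections fill the second row?**

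- Section 7.2 refers to the online CRF without showing its content.
- Section 15 makes site investigators responsible for adverse drug event data, and the principal investigator for collecting adverse events. It gives no scope, seriousness threshold or procedure.
- Section 4.5.2 draws hemoglobin and bilirubin at T1 to T4. No rule turns a laboratory value into a reported event.
- Section 9.2 has the DSMB review deidentified data but does not specify the data set. The charter is a separate document.

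None of these supplies a recording rule.

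**Step 3. Trace two examples**

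Hemolysis is described in 8.1.2 for vitamin C in G6PD deficiency. Only a known history is excluded, and 4.5.2 lists no G6PD test, so undiagnosed cases can enter. Hemolysis is not among the five categories. If a related case is judged consistent with the reference safety information, no rule records it. If it is judged inconsistent in nature, severity or outcome, it goes to the CRF, and to the DSMB within 7 days. The outcome turns on a reference that is not named.

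Gastrointestinal bleeding is also unlisted; the gastrointestinal row in 5.4.2 is a site of new infection. It is the weaker example, because 8.1.2 calls it hypothetical and says that sepsis steroid trials have not found it. A site could readily class it as unexpected and report it.

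**Step 4. Compare with the DSMB sentence**

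Section 5.4.1 defines an adverse event as any untoward medical occurrence, whatever its cause. The stated collection rules yield the five categories plus unexpected related serious events. The second set is narrower than the first, so the aggregate review described in 5.4.3 has no procedure behind it.

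**Step 5. Scale, for illustration only**

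The documents give no rate for an expected, unlisted, related serious reaction. With an assumed rate p, the chance of at least one among n active-arm patients is 1 − (1 − p)^n. With 200 patients at 1:1, n = 100 by the end of the trial and about 50/2 = 25 at the first DSMB review. For p = 1% and n = 100: 1 − 0.99^100 = 0.634.

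| Assumed rate | Expected count in 100 | At least one in 25 | At least one in 100 |
|---|---|---|---|
| 0.5% | 0.5 | 12% | 39% |
| 1% | 1 | 22% | 63% |
| 2% | 2 | 40% | 87% |
| 5% | 5 | 72% | 99% |

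**The case against.** The strongest reply is that 5.4.3 states what must be recorded and reported promptly, and does not say that nothing else is recorded. The CRF and the DSMB charter are not in the documents, Section 15 gives sites a wider duty, and the DSMB sentence itself promises everything. Deaths are captured for all participants, and the 120-hour laboratory draw is designated safety monitoring (Section 5.4.5).

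Much of this stands. A reader might infer that only these two streams reach the CRF, that hemolysis or a major bleed would never be seen by the DSMB, or that all such events would be lost at every review. The documents do not support those readings, because the unseen CRF may collect more. Nor do they establish that either example is expected. The reference safety information is not identified, and an unusually severe hemolysis could qualify as unexpected. A count of the risks in 8.1.2 that lack a route would be unsafe for the same reason, and 8.1.2 does not grade those risks as serious.

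The absence of a stated rule survives the reply. General duties and an unseen form do not tell a site what to do with a related, serious, expected, unlisted event, while the one explicit rule on CRF entry is confined to unexpected events.

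**Conclusion.** The point holds as a gap in the written rules. A serious event thought related to study drug, expected and outside the five categories, has no stated route to the CRF or the coordinating center, and the DSMB sentence describes a wider set than the rules collect. Because the deciding reference is not named, sites following the protocol faithfully could handle the same event differently.

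The number of events affected cannot be stated from the documents. The probabilities above rest wholly on assumed rates. They show only that at least one such event in the active arm is plausible if the true rate is near 1%. The conclusion assumes that the current text of 5.4.2 and 5.4.3 is what sites work from. If the CRF already collects every related serious event, the text need only be brought into line with it. This is a cheap improvement that should be made. It does not affect the primary analysis.

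**What to change.** In Section 5.4.3:

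- Require every serious adverse event thought related to study drug to be recorded on the CRF, whether expected or not.
- Include these events, by coded arm, in each 50-patient DSMB report.
- Keep unexpectedness only as the filter for expedited reporting to the DSMB, IRB, FDA and sites.
- Reword the aggregate-review sentence to the set actually collected: the 5.4.2 events plus all related serious events. Without this change the added recording would still fall short of every adverse event.

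In Section 5.4.1, name the reference safety information.

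A reasonable extra is to add hemolysis, and optionally gastrointestinal bleeding, to the 5.4.2 list, collected in both arms regardless of attribution. Hemoglobin and bilirubin are already drawn at T1 to T4.

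While the list is open, the sodium entries need reconciling. Section 8.1.2 names hyponatremia as a hydrocortisone risk, the protocol's 5.4.2 lists hypernatremia above 150 mmol/L, and the current SAP text labels that same threshold hyponatremia.

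The cost is a few sentences, one or two CRF rows if the extra is taken, and a small increase in site data entry. Expedited-reporting rules are unchanged, and collection of every unrelated ICU event is not proposed.

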### 5.4.5 Safety Monitoring Labs

As detailed above, safety monitoring labs will be obtained at 120-hours, after completion of the study protocol.

## 6. SAMPLE SIZE CALCULATION AND STATISTICAL ANALYSIS PLAN

### 6.1 Sample size calculation

The study has been powered to have at least 80% power for the primary outcome and all key secondary outcomes as follows:

**SOFA Score:** Based on preliminary data, we conservatively anticipate a decrease in SOFA score of 6 (standard deviation [SD]: 4) in the treatment group and 4 (SD: 2) in the placebo group. With these estimates, enrollment of **200 participants (100/arm)** at an alpha of 0.05 and using a t-test with unequal variance, the trial will provide > 99% power to detect a statistical significant difference between groups.

**Kidney Injury:** Based on preliminary data from our study of vitamin B1 in septic shock, we anticipate that 30% of participants in the treatment group and 55% in the placebo group will have renal failure which will result in a 94% power for this outcome. This calculation and following calculation were performed using the Fisher's exact test.

**Mortality:** Based on preliminary data, we anticipate that the control group will have a mortality of 40%. We estimate a treatment effect of 50% (risk ratio: 0.50) resulting in a mortality of 20% in the treatment group. With these estimates, 182 participants will lead to 80% power. To further increase

the trial's power and due to potential loss-to-follow-up, we will aim to enroll 200 participants. These estimates are conservative compared to the Marik et al. study which found a treatment effect corresponding to a risk ratio of 0.21 which persisted in adjusted analysis.

## Sample Size Adjustment

If after 100 patients are enrolled, the overall change in SOFA score is less than anticipated in the above power analysis and/or the renal failure event rate or mortality rate is lower than predicted, the enrollment target of 200 patients may be adjusted accordingly so as to improve power for the primary outcome and all key secondary outcomes at the end of the trial period. Specifically, we will aim to maintain  $\geq 90\%$  power to detect a 2-point difference in  $\Delta$ SOFA score (using variance seen for the full cohort) and  $\geq 80\%$  power to detect a 50% treatment effect on mortality. Whether to increase the study sample size, and the degree of sample size increase, will be decided on by the blinded Steering Committee who will not have access to data stratified by treatment group. The Steering Committee will take into account logistical and financial considerations when updating the enrollment target.

## 6.2 Statistical analysis plan

### 6.2.1 General considerations

The statistical analyses and reporting will adhere to the CONSORT guidelines. All tests will be two-sided, a p-value  $< 0.05$  will be considered significant, and all confidence intervals will have 95% coverage. All analyses will be conducted on a modified intention-to-treat basis only including participants receiving at least the first dose of the study medications. In a double-blind trial, this approach is unbiased while increasing precision. The two groups will be compared in relation to baseline characteristics using descriptive statistics.

The persons conducting the statistical analysis will be blinded to the randomized allocation. Groups will be designated as "A" and "B" until all pre-specified analyses are performed and shared with all authors and the Data Safety Monitoring Board.

### 6.2.2 SOFA score and renal failure

The change in SOFA score will be calculated and compared between groups using the Wilcoxon Rank Sum test (if the change is not normally distributed) or by a t-test if the change is approximately normally distributed. Fisher's exact tests will be used to compare the incidence of renal failure during the index ICU stay.

If a participant expires prior to the 72-hour time point, SOFA scores will be imputed based on a pre-defined plan as follows. If a participant expires before 24-hours has elapsed, a 20% increase from baseline will be imputed. If a participant expires between 24-hours and 48-hours, a 15% increase from the 24-hour time point will be imputed. If a participant dies between 48-hours and 72-hours, a 20% increase from the 24-hour time point will be imputed. Sensitivity analyses will be performed using various other imputation techniques. Specifically, we will perform 1) a sensitivity analysis in which the worst possible SOFA score (score of 24) is imputed for those participants who expire, 2) a sensitivity analysis in which the last SOFA score for participants who expire will be carried forward, and 3) a sensitivity analysis in which only those patients who survive to 72-hours are included. These sensitivity analyses were chosen to model 'worst-possible' and 'best-possible' scenarios. For the secondary outcome of renal failure, participants who expire during their ICU stay will be assessed to have developed renal failure if they demonstrated any degree of unresolved KDIGO acute kidney injury prior to death. If there was no evidence of acute kidney injury prior to death or if kidney injury had fully resolved, these participants will be assessed as not having developed renal failure.

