### **2.2 Allocation**

Participants will be randomized in a 1:1 ratio to either the combination of vitamin C, hydrocortisone, and vitamin B1 or placebo in blocks with random sizes of 2 or 4. The randomization will be stratified according to site. An independent statistician will create the randomization list using a random number generator. The complete list will only be shared with an independent pharmacy consultant, who will not be involved in clinical care. The pharmacy consultant and the independent statistician will both store the randomization list. The research pharmacy at each enrolling site will receive a site-specific randomization list.

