### 5. OUTCOMES

#### 5.1 Definitions

##### 5.1.1 Primary Outcome

The primary outcome will be the absolute change in the Sequential Organ Failure Assessment (SOFA) score from enrollment (time=0) to 72 hours after drug administration. The SOFA score will be defined using a modification in which the SaO2/FiO2 ratio is substituted for the PaO2/FiO2 ratio as has been previously described. This modified score will be used so that participants without an existing arterial catheter can be spared arterial puncture.

Points	SaO 2 */FiO 2 §	Blood Pressure	GCS 	Bilirubin (mg/dL)	Creatinine (mg/dL)	Platelets (x10  µL)
1	<400	< 70 mm/Hg	13–14	1.2–1.9	1.2 – 1.9	<150
2	<326	dopamine ≤ 5 µg/kg/min or dobutamine (any dose)	10–12	2–5.9	2.0 – 3.4	<100
3	<236 (and receiving invasive or non-invasive mechanical ventilation)	dopamine > 5µg/kg/min, epinephrine/norepinephrine ≤ 0.1 µg/kg/min	6–9	6–11.9	3.5 – 4.9 Or UOP † <500ml/day	<50
4	<151 (and receiving invasive or non-invasive mechanical ventilation)	dopamine > 15, epinephrine/norepinephrine > 0.1 µg/kg/min	<6	>12	> 5.0 UOP † <200ml/day Or receiving renal replacement therapy	<20

\*SaO2=Oxygen saturation (%); § = Fraction of inspired oxygen (%); || = Glasgow Coma Scale; † = Urine Output

FiO2 will be determined by using either the set FiO2 (for patients receiving invasive or non-invasive mechanical ventilation) or by adding 3% FiO2 for each liter/minute of supplemental oxygen added up to 100% FiO2 (for patients not receiving mechanical ventilation). Patients with an SaO2/FiO2 ratio <236 who are not receiving invasive or non-invasive mechanical ventilation, will be assigned a score of 2.

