## 11. TIMELINE AND ENROLLMENT

### 11.1 Timeline

### 11.2 Screening & Enrollment

Enrollment at each site will be continuously monitored by the site investigator and the principal investigator. Each site will be expected to maintain a screening log including all participants who meet all eligibility criteria at that site. A standardized screening log will be provided to each site via RedCap Cloud—thus allowing for continuous updating of the screening log and will allow capture of all screening failures.

Enrollment will be competitive (i.e. without specific enrollment caps). Number of enrollments at each site will be shared with all sites on a monthly basis. Sites will be expected to complete all elements of the online CRF within 48-hours of each time point. In the case that a site continuously underperforms despite troubleshooting and feedback, the steering committee will evaluate whether enrollment will continue at that site.

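### The primary SOFA comparison is not tied to one test or one effect estimate: an undefined normality judgement picks the test, and neither baseline SOFA (as a covariate) nor site enters it

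*Protocol*

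**What the plan says.** Protocol 5.1.1 defines the endpoint: "The primary outcome will be the absolute change in the Sequential Organ Failure Assessment (SOFA) score" between enrollment and 72 hours. Under 6.2.2 this change is to be "compared between groups using the Wilcoxon Rank Sum test (if the change is not normally distributed) or by a t-test" when it is close to normal. No normality test, cut-off, choice of pooled or per-arm assessment, or timing is given. Section 6.2.2 of the SAP has the same text and adds nothing.

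Section 6.2.1 states that "all confidence intervals will have 95% coverage", but 6.2.2 does not say which SOFA quantity an interval would describe. Other outcomes are fixed more firmly. Section 6.2.3 names a hazard ratio for mortality and says what to report if proportional hazards fails. Section 6.2.4 settles on the rank test in advance for lengths of stay and for ventilator- and shock-free days.

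The sizing text is more specific than the analysis text. Section 6.1 assumes mean falls of 6 (SD 4) and 4 (SD 2), "using a t-test with unequal variance". The Sample Size Adjustment text aims for at least 90% "power to detect a 2-point difference in" the change score.

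On design variables, 2.2 says "The randomization will be stratified according to site", but no analysis in 6.2 mentions site. Baseline SOFA is subtracted to form the change and defines an exploratory subgroup (9 or more) in 6.2.5. It is not a covariate.

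**The concern.** Two analysts who follow 6.2.2 in good faith can report different tests and different quantities for the primary outcome. One may give a t-test with a mean difference, the other a rank test with no stated estimate. A rank-test p-value does not by itself say how many SOFA points separate the arms, which is the scale on which the trial was sized. Where the true effect is smaller than planned, the declared significance can also depend on which test was picked. The protocol allows for a smaller effect in its sample-size adjustment.

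The lesser part is efficiency. A baseline value and a stratification factor are both collected, and the comparison adjusts for neither.

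**Working it through.** **1. The plan's own figure.** Inputs from 6.1: 100 per arm, SDs 4 and 2, difference 2, two-sided 0.05.

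- SE = sqrt(16/100 + 4/100) = sqrt(0.20) = 0.447.
- Welch df = 0.20² / [(0.16² + 0.04²)/99] = 145.6.
- Noncentrality = 2/0.447 = 4.472, giving power 99.35%. The stated figure of more than 99% is confirmed.
- With the same SE, the 95% CI half-width is 0.884 and power at 1 point is 60.3%.

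**2. How far the two tests can part.** Simulated falls were N(4+d, SD 4) against N(4, SD 2), rounded to whole points, 100 per arm, 20,000 trials per effect d, with no deaths modelled.

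| True effect d (points) | Welch p<0.05 | Wilcoxon p<0.05 | Tests disagree |
|---|---|---|---|
| 0 | 5.1% | 5.9% | 3.2% |
| 0.5 | 19.3% | 19.5% | 7.1% |
| 1 | 60.5% | 58.2% | 10.4% |
| 1.5 | 91.6% | 89.5% | 5.0% |
| 2 | 99.3% | 98.8% | 0.7% |

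With equal SDs of sqrt(10) in each arm, disagreement is 2.0%, 6.7% and 0.4% at 0, 1 and 2 points. Whether the t-test is pooled or Welch hardly matters: those two disagree in at most 0.12% of trials.

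**3. Adding the planned death imputation.** One run of 4,000 trials had 10% early deaths, all imputed at baseline plus 20%, with baseline mean 10 and SD 3. The death rate and baseline values are assumptions; the documents give neither. Disagreement was 2.9%, 8.6% and 3.4% at 0, 1 and 2 points.

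**4. Why these are upper bounds.** They assume that one analyst uses each test. In a run at 1 point without deaths, Shapiro-Wilk applied per arm and Shapiro-Wilk applied to pooled data led to different conclusions in 1.0% of trials. A formal test and a loose skewness rule (absolute skewness above 1) differed in 9.4%.

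**5. What adjustment could gain.** With the planned SDs, the average arm variance is (16+4)/2 = 10. For a common slope b of change on baseline and baseline SD s, the variance ratio is 1 − b²s²/10. With s = 3 (assumed):

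- b = −0.2: 1 − 0.04×9/10 = 0.96
- b = −0.35: 1 − 0.1225×9/10 = 0.89
- b = −0.5: 1 − 0.25×9/10 = 0.78

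The model proposed under the fix was simulated with 13 unequal sites, blocks of 2 or 4, site intraclass correlation 0.05 (assumed), site fixed effects, HC3 standard errors and 3,000 trials per setting. It gave about 0.97, 0.89 and 0.79 without deaths. With 10% deaths imputed as in step 3 it gave about 1.00, 0.96 and 0.89 (range 0.88 to 1.00). An imputed rise proportional to baseline works against a negative slope in survivors.

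Applied to the planned SE, a ratio of 0.88 gives a half-width of 0.884×sqrt(0.88) = 0.83 and power of about 66% at 1 point. A ratio of 1.00 leaves 0.884 and 60%. If the deaths are instead added on top of SDs 4 and 2, a 1-point effect is diluted to 0.9, and power is 41–43% for Welch and 41–46% adjusted.

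**The case against.** The strongest reply is that the intended analysis can be read from the rest of the document. Section 6.1 points to an unequal-variance t-test, and 6.1 with the adjustment text points to a mean difference in points. An unadjusted comparison of change in a randomized trial is valid, and "The persons conducting the statistical analysis will be blinded to the randomized allocation", so nobody can choose a test by direction. At the planned effect both tests have about 99% power.

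Most of this stands, but it does not close the gap. Section 6.2.2 makes the t-test conditional and attaches no estimate to a rank-test result. Masked labels hide direction, but both p-values remain visible, so masking does not fix the test in advance.

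It is also fair to say that adjustment is partly a matter of preference. Its inputs are assumed. A different assumption set (equal SDs at both times, baseline-to-72-hour correlation 0.3 to 0.7) gives variance ratios (1+rho)/2 of 0.65 to 0.85, which do not overlap 0.88 to 1.00. The documents therefore do not determine the gain. At slope −0.2 with deaths, the robust interval is slightly wider than Welch (half-width 1.02 against 1.00). Under no effect the proposed model rejects in 3.5–4.5% of trials against 4.1–5.0% for Welch (Monte Carlo SE 0.4), so it may be a little conservative.

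**Conclusion.** The point holds as a gap in pre-specification, with a possible small loss of precision. The test is left to an unstated criterion, no SOFA estimate is named, baseline SOFA is not a covariate and site is not used. In the setting with planned SDs and no deaths, the open choice could change significance in at most about 0.7% of trials at 2 points, 10% at 1 point and 3% at no effect. With 10% imputed deaths the 2-point figure is about 3%. The precision gain rests on assumed baseline SD, slope, death rate and site correlation; with imputed deaths it is modest and may be nil.

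A reader might infer more than the documents support:

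- **That the comparison is biased or the power figure wrong.** It is unbiased, and the figure reproduces.
- **That false positives are materially inflated.** With equal means and SDs 4 and 2, a separate 4,000-trial run rejected in 7.3% when the more favorable test could always be taken, against 5.3% for Welch. With equal SDs it was 6.2% against 5.1%. These are worst cases, and nothing in the plan provides for such picking.
- **That baseline SOFA is ignored.** It is subtracted, and it defines a subgroup of the primary outcome.
- **That one trial in ten would be reported differently.** The 10% applies at half the planned effect and assumes that the analysts choose different tests.

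**What to change.** Before unblinding, replace the conditional rule in 6.2.2 with one primary analysis that applies whatever the distribution: a linear model of 72-hour SOFA (deaths imputed as planned) on arm, baseline SOFA and site as a fixed stratification factor, with heteroscedasticity-robust (HC3) standard errors. Report the adjusted mean difference in SOFA points with its 95% CI.

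Section 11.2 sets no enrollment cap per site, so some sites may be very small, and HC3 is undefined for a site with a single participant. Fix a pooling rule in advance, for example that all sites with fewer than 4 analysed participants form one stratum.

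Keep the rank test, with a Hodges-Lehmann shift, as a sensitivity analysis only. On whole-point scores that shift is coarse: over 1,500 simulated trials at a true 2 points it averaged 2.01, but came out as 1, 2 or 3 points in 14%, 71% and 15% of them.

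The cost is SAP wording and a few lines of code; baseline SOFA and site are already collected. The downside is a little extra analysis work and, if baseline is only weakly related to change, an interval that may be very slightly wider.
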